# 7.9.2 Pharmacodynamic Analysis

Sampling times for collection of samples are listed in Table 7.d.

# Table 7.d Pharmacodynamic Sample Collection

# 7.10 Other Outcomes

Not applicable.

# 7.11 Safety Analysis

Safety analyses include evaluations of AEs, clinical laboratory results, vital signs results and 12-lead ECG results. All summaries of safety data are based on subjects included in the Safety Analysis Set. The safety data will be summarized by placebo, each TAK-020 dose level and TAK-020 overall, where appropriate, for the SRD and MRD portions of the study. Placebo data will be pooled across the cohorts in each part.

# 7.11.1 Adverse Events

A TEAE is defined as any AE, regardless of relationship to study drug, which occurs on or after the first dose of study drug and no more than 30 days after receiving the last dose of study drug (onset date – date of last dose +  $1 \le 30$ ). A TEAE may also be an event or condition reported prior to the date of first dose, which worsens in intensity after administration of study drug. A PTE is defined as any adverse event that occurs or worsens after the subject has signed informed consent and before the first dose of study drug.

All AEs will be coded by system organ class (SOC) and preferred term (PT) using MedDRA, version 19 or higher.

Summary tables will be generated for AEs. TEAEs and PTEs will be presented by pooled placebo, each TAK-020 dose level and TAK-020 overall. The following summary tables will be generated separately for SRD and MRD:

- Overview of TEAEs, including number of subjects and events.
- TEAEs by SOC and PT, including number of subjects and events.
- Subject mappings for TEAEs by SOC and PT.
- TEAEs by PT.
- Non-Serious TEAEs by SOC and PT.
- Relationship of TEAEs to study drug by SOC and PT.
- Drug related TEAEs by SOC and PT.
- Intensity of TEAEs by SOC and PT.
- Intensity of drug related TEAEs by SOC and PT.
- PTEs by SOC and PT.
- Serious PTEs by SOC and PT.

TAK-020-1001	Page 21 of 31
Statistical Analysis Plan Final	22 May 2017

If a subject has more than 1 AE that codes to the same level of a MedDRA term, the subject will be counted only once for that level, where applicable, using the most extreme incidence (related or more severe in intensity).

All AEs will be presented in the data listings.

# 7.11.2 Clinical Laboratory Evaluations

All clinical laboratory evaluations (hematology, chemistry and urinalysis) will be summarized. Renal safety biomarkers will be summarized separately.

Clinical laboratory tests will be summarized using descriptive statistics (N, mean, median, SD, minimum, and maximum) for baseline, post-baseline, and change from baseline values by treatment regimen and study visit for both SRD and MRD using the Safety Analysis Set. Unscheduled laboratory assessments that are collected post first dose of study drug will be excluded from the summary statistics. Only the scheduled safety laboratory results within 7 days of the last dose of study drug will be included in the summary. Note that urinalysis parameters with character results, such as protein and nitrite, will only be listed.

Individual results for hematology and chemistry laboratory tests that meet the Takeda predefined laboratory markedly abnormal value (MAV) criteria in Appendix B will be presented in a data listing. If a subject has a MAV for a particular laboratory parameter at a visit, all visits for that subject for that parameter will be listed. The number and percentage of subjects with at least 1 postdose MAV during treatment will be summarized for each laboratory parameter by pooled placebo, each TAK-020 dose level and TAK-020 overall. The mapping of subjects who meet the MAV criteria will also be presented. All postdose observations, including those at unscheduled visits, will be considered to determine if a subject had a MAV during treatment.

Clinical laboratory tests will be summarized using Takeda Standard International System of Units (SI) units. For test results not in SI units, the conversion to SI units will be done in ADaM datasets using the known conversion factors. All laboratory test parameters will be displayed in individual subject data listings using both SI and conventional units (CV).

Clinical laboratory results for all subjects in the safety analysis set will be summarized separately for the SRD and MRD portions of the study.

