#### 7.4 **Diet, Fluid, and Activity Control**

Subjects will be confined to the clinic for the duration of each treatment period: Part 1, Day -1 through Day 5, Part 2, Day -1 through Day 10.

TAK-020	
Study No. TAK-020-1001	Page 37 of 101
Protocol Incorporating Amendment No. 4.0	27 March 2017

During the confinement period, subjects will be given a menu for the dosing period that includes 3 meals and an evening snack, each containing approximately 30% fat (relative to the total calories). On dosing days, breakfast will not be served. For Part 1 of the study, the meals served on the day of dosing should be identical for each cohort in the study. For Part 2 of the study, meals served on the PK assessment days (Days 1 and 9) should be identical for each cohort, M eals on other days should be standardized to ensure comparability if options are provided (consistent protein, carbohydrates, and fat content).

The study menu should be recorded and submitted to the study file with a copy provided to the sponsor prior to the start of the study. The meal start and stop times and percentage of the meal consumed will be recorded in the source and appropriate eCRF for all meals served on PK assessment days, Day 1 for Part 1 of the study (SRD), and Days 1 and 9 for Part 2 of the study (MRD).

If a blood draw or any study procedure coincides with a meal, the blood draw will take precedence followed by the study procedure and then the meal.

During the SRD arm of the study, Part 1, TAK-020 and placebo will be administered on Day 1 with 240 mL of water after a fast of at least 10 hours. Subjects will continue to fast for an additional 4 hours after dosing. Subjects may consume water ad libitum with the exception of 1 hour before and 1 hour after drug administration.

During the MRD arm of the study, Part 2, TAK-020 and placebo will be administered on Days 1 and 3 through 9 with 240 mL of water after a fast of at least 10 hours. Subjects will continue to fast for an additional 4 hours after dosing. Subjects may consume water ad libitum with the exception of 1 hour before and 1 hour after drug administration. The dosing regimen and diet should be consistent on each day of the study.

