#### **Study Schematic for Part 2**

Screening	Check-in	Dose	Washout	Dose	Check-out	Follow-up (a)
Day -28 to -2	Day -1	Day 1	Day 2	Days 3-9	Day 10	Day 17 (±2)

(a) All subjects will return to the unit and complete hematology and serum chemistry tests, vital signs, concomitant medications, and AE assessment.

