# 7.1.3 Definition of Study Visit Windows

There will be no visit windowing.

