# 7.11.3 Vital Signs

Vital signs measurements include systolic and diastolic blood pressure, pulse, body temperature and respiratory rate. Each vital signs measurement will be summarized using descriptive statistics (N, mean, SD, median, minimum and maximum) for baseline, postdose, and change from baseline to postdose values. Summaries will be presented separately for SRD and MRD by pooled placebo and each TAK-020 dose level.

Individual results for vital sign measurements that meet the Takeda predefined vital signs MAV criteria in Appendix C will be presented in a data listing. If a subject has a MAV for a particular vital sign parameter at a visit, all visits for that subject for that parameter will be listed. The number and percentage of subjects with at least 1 postdose markedly abnormal vital sign

TAK-020-1001	Page 22 of 31
Statistical Analysis Plan Final	22 May 2017

measurement during treatment will be summarized by pooled placebo, each TAK-020 dose level and TAK-020 overall. The mapping of the subjects who meet the MAV criteria will also be created. All postdose observations, including those at unscheduled visits, will be considered to determine if a subject had a MAV during treatment.

All vital sign measurements will be listed by subject in the data listings and markedly abnormal values will be flagged.

Vital signs results for all subjects in the safety analysis set will be summarized separately for the SRD and MRD portions of the study.

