# Part 2 (MRD)

	Screening	Check-in	Treatment	Washout	Treatment	Check-out	Early Termination	Follow-up Visit
	Dave -28	CIICCK-III	Treatment	washout	Treatment	Check-out	Termination	Day 17
Study Day:	to -2	Day -1	Day 1	Day 2	Day 3-9	Day 10	(a)	$(\pm 2)$ (b)
Confinement		Х	Х	Х	X	Х		
Informed consent	Х							
Inclusion/exclusion	Х	X						
criteria								
Demographics and medical history	Х	X						
Medication history	Х							
Physical examination	Х		X (c)	Х	Х	Х	Х	
Vital signs (d)	Х	Х	Х	Х	Х	Х	Х	Х
Weight, height, and BMI (e)	Х	X				Х	Х	
Concurrent medical conditions	Х	X						
Concomitant medications (f)	Х	X	Х	Х	X	Х	X	Х
Clinical laboratory tests (g)	Х	X		X	X	X	Х	X (s)
Hepatitis panel	Х							
HIV screening	X							
TB screening	X							
Pregnancy test (hCG) (h)	Х	X				X	X	
Urine drug/alcohol/cotinine screen	Х	X						
ECG (i)	Х	Х	Х	Х	Х	Х	Х	
Telemetry (j)			Х		X			
PGx DNA sample collection (k)			Х					
PGx RNA sample collection (l)			Х		X			
PK blood collection (m)			Х	Х	X	Х	Х	
PK urine collection (n)			X	Х	X	Х	Х	
CCI			1		1	1		
CCI								
Dispense study medication			X		X			
PTE assessment (r)	Х	X	Х					
AE assessment			Х	Х	X	Х	X	Х

Footnotes are on the next page.

TAK-020-1001	Page 28 of 31
Statistical Analysis Plan Final	22 May 2017

(a) Conduct procedures for subjects discontinued early. The PK sample collection should be collected at the Early Termination Visit, if possible. For example, collect samples if early withdrawal is due to an AE, and/or if several hours elapsed since last blood draw].

(b) All subjects will return to the unit and complete Hematology and Serum Chemistry tests, vital signs, concomitant medications, and AE assessment.

(c) The physical examination can be conducted within 24 hours prior to study drug administration.

(d) Vital signs (oral temperature, sitting pulse, and blood pressure) will be collected at Screening and Check-in (Day -1) and on Day 1 at predose (0 hours) and 1, 4, 12, 24 hours postdose, then twice daily until Study Exit (Day 10) or Early Termination and once during the Follow-up visit.

(e) Height will only be collected at Screening.

(f) Record all medications (other than study drug) from Screening and throughout the study.

(g) Clinical laboratory tests (hematology, serum chemistries, and urinalysis) will be collected at Screening, Day -1, Days 2, 3, 5, 8 and prior to check-out (Day 10) or Early Termination. Laboratory samples will be taken following a minimum 10-hour overnight fast

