(h) Pregnancy test (hCG) will be performed for all female subjects.

(i) Triplicate 12-lead ECGs printed in standard format, will be collected at Screening, Check-in (Day -1), Day 1 predose (0 hours) and at 1, 4, 12, and 24 hours postdose, Days 3, 5, 9, 10 at predose (0 hours) or Early Termination.

(j) Telemetry will be performed approximately 2 hours predose until 12 hours postdose on Days 1 and 9 only. Ten (10) sec triplicate ECGs will be extracted at PK time-points for manual reading and precise ECG reading including QT interval measurement.

(k) One blood sample (6 mL) will be collected prior to dosing on Day 1.

(I) Two whole blood samples (2.5 mL per sample) will be collected at predose on Days 1, 3 and 9.

(m) Blood samples for PK analysis will be collected at predose on Day 1 (within 30 minutes prior to dosing) and at 0.25, 0.5,

0.75, 1, 2, 3, 4, 6, 8, 10, 12, 16, 24, 36, and 48 hours postdose and at predose on Day 9 (within 30 minutes prior to dosing) and at 0.25, 0.5, 0.75, 1, 2, 3, 4, 6, 8, 10, 12, 16, and 24 hours postdose.

(n) Urine samples for PK analysis will be collected on Day 1 and Day 9 at predose (-12-0), and 0-6, 6-12, 12-24 hour postdose intervals.

(r) PTEs will be collected from signing of informed consent up until dosing on Day 1

(s) Hematology and Serum Chemistry only.

TAK-020-1001	Page 29 of 31
Statistical Analysis Plan Final	22 May 2017

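### The 7-day limit in SAP 7.11.2 removes the scheduled Part 2 Follow-up laboratory results (Day 17, 8 days after the last dose) from the by-visit summary, wholly or selectively

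*SAP*

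**What the plan says.** SAP 7.11.2 provides descriptive statistics for baseline, post-baseline and change from baseline by regimen and visit, separately for the two parts. It excludes unscheduled postdose results and then adds: "Only the scheduled safety laboratory results within 7 days of the last dose of study drug will be included in the summary". It gives no reason for the limit and does not define how the days are counted. SAP 7.1.3 states "There will be no visit windowing".

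On timing, Protocol 7.4 says that in Part 2 "TAK-020 and placebo will be administered on Days 1 and 3 through 9", so the last planned dose is on Day 9. SAP Table 4.a places Follow-up on Day 17 (±2) and says "All subjects will return to the unit and complete hematology and serum chemistry tests". The Follow-up laboratory entry in the Part 2 schedule (SAP Appendix A) is footnoted "Hematology and Serum Chemistry only". The other Part 2 postdose laboratory days listed there are "Days 2, 3, 5, 8 and prior to check-out (Day 10) or Early Termination".

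Protocol 13.1.5.2 plans a summary of postdose laboratory data by placebo and dose level, with no time limit. SAP 7.13 records no changes.

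**The concern.** Follow-up is a planned visit for every Part 2 subject, yet its target day lies outside the limit. The limit conflicts with the same section's statement that all laboratory evaluations are summarized by visit, and with Protocol 13.1.5.2.

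Two readings are open, and the SAP does not choose between them. Applied by actual date, the rule keeps early attenders and drops everyone else, so the Follow-up row is a subset selected on attendance day. Applied by planned visit, the whole row disappears.

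Other safety data from this visit carry no such limit. Vital signs are taken "twice daily until Study Exit (Day 10) or Early Termination and once during the Follow-up visit", and SAP 7.11.3, where "Each vital signs measurement will be summarized using descriptive statistics", sets no cut-off. Treatment-emergent adverse events count for 30 days after the last dose.

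Safety is the primary objective. Protocol 4.1 describes an irreversible inhibitor that stays bound to its target after plasma levels can no longer be detected. Protocol 6.2 names low serum immunoglobulins as a risk of the mechanism, and liver and kidney as target organs in the rat. Follow-up gives the only scheduled Part 2 laboratory data more than 1 day after the last dose. What would be lost is the group-level view of values and changes by dose and placebo, below the thresholds for a MAV or a clinically significant abnormality.

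**Working it through.** The plan gives no figure on this point to reproduce. The check is day arithmetic.

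**Inputs**
- Last planned Part 2 dose: Day 9 (Protocol 7.4).
- Follow-up: Day 17 ± 2, so Days 15 to 19 (SAP Table 4.a and Appendix A).
- Limit: 7 days (SAP 7.11.2).
- Part 2 maximum: 7 cohorts of 8, with 6 active and 2 placebo in each (SAP 4.4).

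**Days after the last dose.** The plain count is visit day − 9. The SAP's adverse event definition (7.11.1) adds 1. Section 7.11.2 states neither, so both are shown.

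| Follow-up day | Plain count | In summary? | Count with +1 | In summary? |
|---|---|---|---|---|
| 15 | 6 | yes | 7 | yes |
| 16 | 7 | yes | 8 | no |
| 17 (target) | 8 | no | 9 | no |
| 18 | 9 | no | 10 | no |
| 19 | 10 | no | 11 | no |

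Excluded: 3 of 5 permitted days on the plain count, and 4 of 5 with +1. The target day is excluded on both.

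**Other scheduled laboratory visits, for subjects who complete dosing**
- Part 2 check-out: 10 − 9 = 1 day (2 with +1), retained.
- Part 1 check-out: 5 − 1 = 4 days (5 with +1), retained.
- Part 1 Follow-up on Day 14 is a telephone call with no laboratory tests planned for all subjects.

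The effect is therefore confined to Part 2 Follow-up.

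**Share of visits and subjects.** The scheduled postdose Part 2 laboratory visits in SAP Appendix A are Days 2, 3, 5, 8, 10 and Follow-up. That makes 6, of which 1 is affected. Subjects: 7 × 8 = 56 at most (7 × 6 = 42 active, 7 × 2 = 14 placebo).

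**Comparison with the adverse event window.** Onset − 9 + 1 ≤ 30 gives onset ≤ Day 38, so all five Follow-up days fall inside it.

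**What the MAV counts can recover.** SAP Appendix B has 6 hematology and 15 chemistry parameters, 21 in all. None is for immunoglobulins, neutrophils, lymphocytes, INR or aPTT, all of which are in Protocol Table 9.a. These have no MAV count at any visit, so with the limit in place their Follow-up values would have no complete group-level summary.

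**The case against.** The strongest reply is that a near-treatment window for descriptive laboratory tables is a common and legitimate choice, and that no endpoint depends on it. Much of this stands. The primary laboratory endpoint is the MAV count, which considers all postdose observations. All values are listed. Protocol 9.1.8 has clinically significant abnormalities recorded as adverse events. What is at stake is one descriptive row, with 6 active subjects per cohort and no test. But if the window is deliberate, the SAP should say so and say what happens to a visit planned for every subject; at present the rule contradicts its own section and the protocol.

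Other points, and what remains of each:
- **Selective inclusion is not certain.** True: it needs counting by actual date and some attendance on Day 15 or 16. The alternative is loss of the whole row.
- **The +1 count is borrowed from the adverse event definition.** True, but the target day fails without it.
- **Protocol 10.2.1.1 can be read as placing Follow-up 17 (±2) days after the last dose.** On that reading every Follow-up day is outside the limit and the whole row is lost.
- **Missing MAV rows are a separate gap, and dose-limiting toxicities are judged subject by subject.** Both are true. Neutrophils, lymphocytes, INR and aPTT appear in Protocol Table 6.a, which shows their clinical interest; no escalation decision rests on this table.
- **Amendment 4 added Day 17 pharmacodynamic sampling, not safety analyses.** True. It bears on relevance only.
- **SAP 7.11.3 does not promise a Follow-up row for vital signs.** True. It only sets no cut-off.
- **Protocol Table 9.d shows a safety draw on Day 1 and none on Day 8.** The count of 6 visits therefore rests on Appendix A. Table 9.d also includes the Follow-up draw.

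**Conclusion.** The concern holds. As written, SAP 7.11.2 keeps the on-schedule Part 2 Follow-up laboratory results out of the by-visit summary and leaves either no Follow-up row or one made up of early attenders. The size is 1 of 6 scheduled postdose Part 2 laboratory visits, for up to 56 subjects, with 3 of the 5 permitted days (4 with the +1 count) outside the limit.

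This rests on a last dose on Day 9, Follow-up on study Day 17 (±2), and the visit list in SAP Appendix A. The documents give no attendance dates, so no proportion of subjects is estimated. A subject who stopped dosing before Day 9 and attended Follow-up in its window would be further outside the limit.

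The consequence is limited to descriptive summaries. It should be corrected because safety is the primary objective and these are the only scheduled Part 2 laboratory data that show group values more than 1 day after dosing ends.

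**What to change.** For Part 2, replace the 7-day limit with inclusion by scheduled visit through Follow-up (Day 17 ± 2). Tabulate Follow-up as its own visit with change from baseline, labelled as post-treatment, so that the on-treatment rows stay as they are. Part 1 needs no change.

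The same edit should settle two loose ends: whether the rule covers the renal biomarkers, which SAP 7.11.2 summarizes separately and Protocol 9.3.3 collects at Follow-up; and how results are handled for subjects who stop dosing early. If a time limit is kept for the latter, its day count should be defined.

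The core change costs one sentence of SAP text and one more visit row in the Part 2 laboratory tables. The hematology and chemistry samples are already scheduled, so no new data are needed.

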# 6.1.2 Criteria for Stopping Dose Escalation

- 1. Two or more subjects in any single cohort or across more than 1 cohort experience any of the Takeda Medically Significant List events (as outlined in Table 10.a).\*
- 2. Two or more subjects in any single cohort experience alanine aminotransferase (ALT) and/or aspartate aminotransferase (AST) elevations > 3 x upper limit of normal (ULN), irrespective of total bilirubin increase or other lab changes.
- 3. Two or more subjects in any single cohort or across more than 1 cohort experience ALT and/or AST elevations >5 × ULN in the absence of a concomitant bilirubin increase.\*
- 4. One or more subjects in any single cohort or across more than 1 cohort experience ALT and/or AST elevations >3 ×ULN in the presence of a total bilirubin increase >2 ×ULN or an international normalized ratio (INR) >1.5 without findings of cholestasis or other alternate etiology to explain the elevations (ie, "Hy's Law cases").
- 5. Two or more subjects in any single cohort or across more than 1 cohort experience ALT and/or AST elevations >3 ×ULN with the appearance of fatigue, nausea, vomiting, right upper quadrant pain or tenderness, fever, rash and/or eosinophilia (>5%).\*
- 6. Within each dose level, if 2 subjects develop a dose limiting toxicity (DLT) listed in Table 6.a that is confirmed by repeat test if applicable, the subject(s) will be unblinded prior to any dose-escalation safety review meeting. If the unblinded subjects have received TAK-020, no further dosing will occur in that dose level and no further dose escalation beyond that dose level will be allowed.
- 7. Two or more subjects in the same cohort experience the same toxicity graded at least as moderate ( $\geq$  Grade 2) and requiring discontinuation of investigational drug.

\* Please note that the study may be terminated early prior to full attainment of these criteria (eg, if just 1 subject experiences 1 of these events) if warranted by safety data from the other subjects dosed in the study to date.

- In addition to Takeda's standard criteria for study termination, the following stopping criteria will also be implemented in this study for individual subjects:
  - Within each dose level, if at least 1 subject develops a DLT listed in Table 6.a, and confirmed by repeat test, if applicable, the subject will be unblinded prior to any dose-escalation safety review meeting. If the unblinded subject has received TAK-020, no further dosing will occur in that subject.

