Toxicity	Definition
Leukopenia	Total leukocyte count $<2500 \text{ cells/mm}^3$ (2.5×10  /L)
Neutropenia	Absolute neutrophil count $<1500/\text{mm}^3$ (1.5 x $10^9/\text{L}$ )
Thrombocytopenia	Platelet count $<75 \text{ x}10^9/\text{L}$
Lymphopenia	Lymphocyte count <1000 cells/mm  $(1.0 \times 10^9/L)$
Liver enzymes	ALT or AST $>3 \times$ ULN
Renal changes	Serum Creatinine>1.3×ULN
	Or
	eGFR decrease by 30% from Baseline
Abnormal coagulation	INR >2×ULN
	aPTT >2×ULN
	prothrombin time >2×ULN
QT interval with Fridericia correction method (QTcF)	QTcF >500 msec or a change from Baseline in QT/QTcF of >60 ms.
Severe infection	Serious infection requiring hospitalization, intravenous (IV) antibiotics (more than 1 dose), systemic antifungal or antiviral intervention

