# Appendix C Criteria for Identification of Markedly Abnormal Vital Signs Parameters

Parameter	Lower Criteria	Upper Criteria
Heart rate	<50 beats per minute	>120 beats per minute
PR	≤80 milliseconds	≥200 milliseconds
QT Interval	≤300 milliseconds	≥460 milliseconds
QTcB Interval	≤300 milliseconds	≥500 milliseconds OR
		≥30 milliseconds change from baseline and ≥450 milliseconds
QTcF Interval	≤300 milliseconds	≥500 milliseconds OR
		≥30 milliseconds change from baseline and ≥450 milliseconds
QRS	≤80 milliseconds	≥180 milliseconds

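### The ECG MAV count takes a pre-existing PR of 200 ms or more as a postdose finding; secondarily, no planned table counts subjects who meet the DLT thresholds

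*SAP*

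**What the plan says.** SAP 5.1 makes the number and percentage of subjects with a postdose MAV a primary safety endpoint, separately for laboratory tests, vital signs and ECGs. The laboratory count rests on results from "laboratory tests that meet the Takeda predefined laboratory markedly abnormal value (MAV) criteria in Appendix B" (SAP 7.11.2). The ECG count rests on the ECG criteria table, which the SAP lists as Appendix D. In both, all postdose observations count, including unscheduled ones. For ECGs, one qualifying tracing in a triplicate is enough (SAP 7.11.4).

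The PR criterion is an absolute 200 ms or more. Protocol 7.2, exclusion criterion 17, admits PR from 120 to 220 ms. Baseline is the last observation before first dose (SAP 7.1), but no MAV rule refers to MAV status at baseline.

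Protocol Table 6.a is a separate list of dose-limiting toxicities. Under stopping criterion 6 (Protocol 6.1.2), two subjects at a dose level with a DLT, "confirmed by repeat test if applicable", are unblinded; if they received TAK-020, dosing at that level ends and "no further dose escalation beyond that dose level will be allowed". The list includes "eGFR decrease by 30% from Baseline" and "a change from Baseline in QT/QTcF of >60 ms". The SAP does not mention DLTs.

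**The concern.** Where the protocol gives a numeric entry limit (PR, QTcF, ALT/AST), PR is the only parameter whose eligible range runs into its MAV range. A subject can therefore arrive already meeting the criterion and be reported as a postdose ECG MAV with nothing having changed. With six active subjects per level, one such subject moves the reported incidence from 0% to 17%, and the table does not show whether the finding is new.

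The DLT gap points the opposite way. The thresholds that govern escalation and the thresholds that feed the primary tables are different lists. A reader of the planned tables could not see how many subjects at a dose level met the former.

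**Working it through.** The plan states no figure to reproduce here; the sample size was not based on power.

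**PR**

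Inputs from the documents:
- Eligible PR is 120-220 ms; the MAV is 200 ms or more; any single tracing counts.
- Postdose triplicates (Protocol 9.1.11.1): Part 1 at 1, 4, 12, 24, 48, 72 and 96 h, which is 7. Part 2 at 1, 4, 12 and 24 h after the Day 1 dose, plus Days 3, 5, 9 and 10, which is 8.

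Assumptions: stable true PR, no drug effect, normal reading error with SD 4-8 ms, within-triplicate correlation ρ from 0 to 0.8, time points independent.

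At a true PR of exactly 200 ms the SD drops out. The chance that all three tracings of a triplicate fall below 200 is q = 1/8 + (3/4π)·arcsin(ρ), so q = 0.125 at ρ = 0 and 0.346 at ρ = 0.8.
- All-postdose count, Part 1, worst case: 1 − 0.346^7 = 0.999.
- Treatment-emergent count (no baseline tracing meets the criterion): q(1 − q^7), which is 0.125 to 0.346.

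Simulation (40,000 subjects per setting, both parts, one baseline triplicate) agrees and extends this:

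| True PR (ms) | Counted, all postdose | Counted, treatment-emergent |
|---|---|---|
| 195 | 0.749-0.999 | 0.393-0.667 |
| 200 | 0.999-1.000 | 0.124-0.349 |
| 205 | 1.000 | 0.001-0.148 |
| 210 | 1.000 | 0.000-0.043 |
| 220 | 1.000 | 0.000-0.001 |

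One subject is 1/6 = 16.7% of a dose level (exact 95% CI 0.4% to 64.1%), against 0/6 (0% to 45.9%). The documents do not give the prevalence p of such subjects. Purely for scale, p of 0.5% to 5% gives 128p = 0.64 to 6.4 subjects over both parts (72 + 56 = 128), and 1 − (1 − p)^6 = 3.0% to 26.5% for at least one in a given level.

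**DLT thresholds against MAV criteria**

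| Table 6.a row | DLT | MAV | DLT possible without a MAV? |
|---|---|---|---|
| Leukopenia | <2.5×10^9/L | <0.5×LLN | If LLN is below 2.5/0.5 = 5.0 |
| Neutropenia | <1.5×10^9/L | none | Yes |
| Thrombocytopenia | <75×10^9/L | same | No |
| Lymphopenia | <1.0×10^9/L | none | Yes |
| Liver enzymes | >3×ULN | same | No |
| Renal | creatinine >1.3×ULN, or 30% eGFR fall | creatinine >2.0 mg/dL | Yes through eGFR; through creatinine if ULN is below 2.0/1.3 = 1.54 mg/dL |
| Coagulation | INR, aPTT or PT >2×ULN | fibrinogen only | Yes |
| QTcF | >500 ms, or change >60 ms | ≥500 ms, or ≥450 ms with change ≥30 ms | Yes through change: baseline <390 ms and postdose <450 ms |

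Four of the seven laboratory rows escape without any outside figure, and leukopenia is a fifth if the local LLN is below 5.0.
- **eGFR.** If eGFR varies as creatinine to the power −k, with k from 1.0 to 1.2 (assumed), a 30% fall is a creatinine rise of 0.7^(−1/k) = 1.43 to 1.35 times. Any baseline below 2.0/1.43 = 1.40 mg/dL then stays under the MAV limit.
- **QTcF.** The MAV's "≥30 milliseconds change from baseline" counts only together with a value of at least 450 ms. A rise from 380 to 445 ms is 65 ms: a DLT, not a MAV.

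Two DLTs on TAK-020 are 2/6 = 33.3% (exact 95% CI 4.3% to 77.7%), possibly beside 0/6 MAVs.

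The by-visit summaries do not supply the count. They omit unscheduled results, and "Only the scheduled safety laboratory results within 7 days of the last dose of study drug will be included in the summary". Nominal Part 2 follow-up is Day 17 − Day 9 = 8 days after the last dose (6 to 10 days over the ±2-day window).

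**The case against.** On PR, the same rule applies to placebo and subjects are randomized, so pre-existing long PR adds noise rather than a systematic bias against TAK-020. SAP 7.11.4 lists every visit for a subject with an ECG MAV, so a careful reader can find the baseline value, and change from baseline in PR is summarized. All of that stands, but it leaves the reader to rebuild by hand what the primary table should show. The reading SD, correlation and prevalence are assumptions. In the copy read here the ECG table follows the vital-signs heading, so a footnote qualifying the PR row cannot be wholly excluded; the text of 7.11.4 contains no such qualifier.

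On DLTs, a reader might infer that the MAV appendices are wrong, or that a stopped dose level would look clean in the report. The documents support neither.
- Nothing in the protocol requires MAVs to contain DLTs, and there is no DLT-incidence endpoint. The SAP's primary endpoints match the protocol's.
- Protocol 6.2 reports all nine Part 1 doses and Part 2 doses up to 25 mg as tested, safe and well tolerated. A criterion 6 stop is therefore mainly a prospect for Part 2 Cohorts 5-7.
- Protocol 10.1.3 treats a laboratory or ECG change as clinically significant if action is required, and 6.1.2 ends dosing for a subject on TAK-020 with a DLT. Such an event should normally appear as a TEAE, which is another primary endpoint, and in disposition. A DLT first seen after the last dose still depends on judgement.
- Criteria 2-5 turn on ALT/AST above 3×ULN, which is always a MAV. Cohort-by-cohort review of the data is unaffected.

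What remains is narrower: no planned table gives the number of subjects per dose level who met the thresholds.

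**Conclusion.** The PR point holds as a cheap improvement. The stated rule puts pre-existing findings into a primary safety endpoint, and a subject with true PR of 200-220 ms is almost certain to be counted. That result needs only stable PR and ordinary reading error. The 17% per subject is arithmetic on six active subjects. The number of such subjects is unknown, so one might infer that the endpoint will be badly inflated, but the documents do not show that.

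The DLT point holds as a reporting gap, not an error. At least four of seven laboratory rows and the QTcF change limb can be met without a MAV. Leukopenia and the creatinine limb depend on local reference limits that the documents do not give.

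**What to change.** Leave the primary endpoint and the MAV appendices as they are, and add two supplementary tables, each by part, for pooled placebo, each dose level and TAK-020 overall.

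1. **Treatment-emergent MAV.** Show n (%) of subjects with a postdose MAV whose criterion was not met on any tracing or value at the SAP baseline, beside the all-postdose count. For ECGs, state that baseline means all three tracings of the last predose triplicate.
2. **DLT thresholds.** Show n (%) of subjects meeting each Table 6.a row postdose, including unscheduled results and the severe-infection row. Show confirmed-on-repeat and already-met-at-baseline separately; otherwise this table would repeat the PR problem, since entry sets no numeric neutrophil or lymphocyte limit.

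The sponsor should also reconcile the DLT and MAV lists or explain why they differ. This review takes no position on which limit is right.

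The cost is a few tables from data already collected and two MAV counts to explain. Chance crossings remain just under a threshold: at a true PR of 195 ms the treatment-emergent count still takes 39-67% of subjects, against 75-100% for the all-postdose count. Both should be read against pooled placebo.
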